## **2.0 Background**

Today in clinical practice, dropout from contact lens wear remains a significant problem, with up to 34% of patients discontinuing lens wear. Contact lens discomfort is one of the main causes of contact lens dropout. There are many factors that may play a role in contact lens comfort, but the primary factor may be the interaction of the eyelid and the contact lens material. It has been proposed that reduced contact lens lubricity, a measure of the friction inherent to a contact lens material, may lead to increased contact lens discomfort. Contact lens lubricity can be described by the coefficient of friction (CoF) of the contact lens material. CoF has been reported to be inversely proportional to reported contact lens comfort; therefore, materials with a higher CoF tend to be less comfortable.

## **FULL PROTOCOL TITLE: The Impact of Contact Lens Coefficient of Friction (CoF) on the Development of Lid Wiper Epitheliopathy (LWE)**

While CoF is a useful laboratory metric, it cannot be measured clinically. Therefore, a clinical corollary for CoF may be useful in determining which contact lens materials will minimize the potential for contact lens dropout. A possible clinical corollary for CoF is Lid Wiper Epitheliopathy (LWE), which has been reported to be related to contact lens discomfort. LWE leads to a loss of superficial epithelial cells in the lid wiper region of the eyelid. If CoF is indeed related to contact lens discomfort, subjects wearing a high CoF lens could potentially develop greater amounts of LWE compared to that observed with a low CoF lens.

While previous studies have determined the amount of LWE present in habitual contact lens wearers and non-contact lens patients, it is currently unknown how quickly LWE may develop in patients after contact lens fitting. Development of LWE in the post-contact lens fitting period may allow clinicians to predict the potential for contact lens discomfort and future dropout. This pilot study will collect data examining the development of LWE in the period immediately following contact lens fitting (2 hours post-fit) and after approximately 1 week of contact lens wear, corresponding to the time for a typical post-contact lens fitting assessment in clinical practice.

### **3.0 Inclusion and Exclusion Criteria**

Potential study subjects must meet the following study inclusion criteria:

1. Must be able to read and understand the study informed consent
2. Must be a minimum of 18 years of age and less than 46 years of age at study enrollment
3. Must be healthy non-soft contact lens wearers (neophytes), or experienced contact lens wearers that have not worn their contact lenses for a minimum of 7 days
4. Have a spherical equivalent refractive error between -0.75 to -6.50DS at the spectacle plane
5. The subject must be able to attend study visits at the prescribed visit times and adhere to the study instructions

Potential study subjects cannot meet any of the following study exclusion criteria:

1. Pregnant and/or lactating females by self-report
2. Presence of current LWE on the upper eyelid (>0.5 in height or width)
3. Has greater than -1.00DC of refractive cylinder
4. Has greater than 1.00D of anisometropia
5. Is aphakic
6. Has clinically significant corneal or conjunctival staining that would prevent contact lens fitting, as assessed with sodium fluorescein dye

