# **FULL PROTOCOL TITLE: The Impact of Contact Lens Coefficient of Friction (CoF) on the Development of Lid Wiper Epitheliopathy (LWE)**

## **1.0 Objectives**

The primary study objectives are to determine the amount of Lid Wiper Epitheliopathy (LWE) induced in subjects after contact lens fitting that do not have LWE at study enrollment. Subjects in the trial will be fit in 2 contact lenses with different coefficients of friction (CoF). One eye will be fit in a contact lens with a low coefficient of friction (Acuvue Oasys®, Johnson & Johnson Vision, Jacksonville FL) while the contralateral eye will be fit in a contact lens with a high CoF (Air Optix® Night & Day® Aqua, Ft. Worth, TX), as reported in the scientific literature. The eye receiving each lens will be assigned randomly. The presence of LWE will be assessed at 2 different time points:

- Approximately 2 hours after contact lens fitting and
- After 7( $\pm 2$ ) days of contact lens wear

**Study Hypotheses:** Contact lenses with a greater coefficient of friction will induce a greater amount of LWE than contact lenses with a lower coefficient of friction. The presence of LWE will be assessed at 2 different study time points. As such, the following hypotheses will be tested:

After one week of contact lens wear

- $H_{01}$ : There is no statistically significant difference in the amount of LWE between contact lenses with different coefficients of friction
- $H_{a1}$ : There is a statistically significant difference in the amount of LWE between contact lenses with different coefficients of friction

After 2 hours of contact lens wear

- $H_{02}$ : There is no statistically significant difference in the amount of LWE between contact lenses with different coefficients of friction
- $H_{a2}$ : There is a statistically significant difference in the amount of LWE between contact lenses with different coefficients of friction

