## **FULL PROTOCOL TITLE: The Impact of Contact Lens Coefficient of Friction (CoF) on the Development of Lid Wiper Epitheliopathy (LWE)**

7. Has significant ocular surface disease (e.g. Sjögren's Disease, Stevens-Johnson Syndrome, etc.) or significant Dry Eye Syndrome
8. Has clinically significant corneal vascularization or central corneal scaring
9. Has active ocular surface infection (e.g. conjunctivitis)
10. Has a positive history of eyelid surgery or trauma
11. Has a positive history of refractive surgery
12. Takes medications that significantly impact contact lens comfort and/or ocular surface health
13. Has taken part in another contact lens or contact lens solution clinical trial within the last 7 days
14. Is unwilling to have eyes photographed or video recorded

Potential subjects will be initially screened for study eligibility through collection of demographic data and medical history. An upper age limit for study inclusion is set at 46 years of age to 1) prevent the inclusion of presbyopic patients (i.e. those that need bifocal glasses), given that the contact lenses used in the study are single vision contact lenses and 2) reduce the number of individuals who would screen fail due to significant dry eye disease. Subjects will complete a questionnaire, the Ocular Surface Disease Index (OSDI), and subjects with a score  $\geq 23$  will be excluded from the study. A slit lamp evaluation will be performed to screen for the presence of LWE of the upper lid and for significant corneal/conjunctival staining that would prevent contact lens fitting. If the subject does not have LWE, the subjects will be refracted to determine eligibility based on their refractive error. If the refractive error is within the study specified inclusion criteria, the subject will be fit into contact lenses.

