### **5.0 Number of Subjects**

The proposed single-site study will be conducted at The Ocular Surface Institute at the University of Houston College of Optometry. Up to 60 subjects will be screened for study inclusion, with the goal of completing 20 subjects. Subjects that screen fail may be rescreened for study inclusion up to 3 additional times at the discretion of the study investigator.

Currently, there is no information on the time from contact lens fitting to the development of LWE. This pilot study is designed to collect data which can be used to determine the sample size required to conduct a larger-scale clinical trial. It is anticipated that enrolling 20 subjects will approach the requirements of the central limit theorem for statistical analysis. Since the subjects in the study will be wearing FDA-approved contact lenses on a daily wear modality (i.e. not sleeping in contact lenses), the study does not present more than minimal risk to the subject and a power analysis is not required.

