### Sequence of Events

## FULL PROTOCOL TITLE: The Impact of Contact Lens Coefficient of Friction (CoF) on the Development of Lid Wiper Epitheliopathy (LWE)

Note: Contact Lens wearing subjects should report to Visit 1 after discontinuing SCL wear for at least 7 days. Subjects should report to the visit wearing their habitual vision correction.

Visit 1.1: Screening, Enrollment and Baseline		
Step	Item	Details
1.1.1	Informed Consent	Review and complete the informed consent form
1.1.2	Subject Demographics	Collect subject demographic data
1.1.3	History	Collect subject history
1.1.4	Concomitant Medications	Collect information on concomitant medications
1.1.5	Habitual Contact Lens Information	For CL subjects, review habitual lens information and verify that they have discontinued lens wear for at least 7 days
1.1.6	Preliminary Review of Inclusion/Exclusion Criteria	Review Inclusion/Exclusion Criteria for subject study eligibility
1.1.7	Distance Visual Acuity	Perform Distance, High Contrast Visual Acuity using Snellen optotype, OD/OS with the patient's habitual correction.
1.1.8	Questionnaires: Ocular Surface Disease Index (OSDI)	All Subjects: Administer the OSDI 
 
• If OSDI scores is <math>\geq 23</math>; skip to 2.9, Final Evaluation
 

1.1.9	Auto-refraction	Perform auto-refraction and record the refractive error and keratometry readings
1.1.10	Oculus Keratograph	Perform the following procedures using Oculus Keratograph, OD/OS 
 
• Non-invasive Tear Break Up Time (NITBUT)
 
• Tear Meniscus Height
 

1.1.11	Phenol Red Thread	Perform Phenol Red Thread test without anesthesia, OD/OS.
1.22	Ocular Surface Tear Collection	Collect 10 $\mu$ L surface tears using a microcapillary tube.
1.1.12	Slit Lamp Exam with vital dye staining/LWE evaluation	Instill 1 drop of NaFL + Lissamine Green Combination Drop, wait 5 minutes, instill an additional drop, wait 1 minute, then evaluate slit lamp findings using the CCLRU grading scale and evaluate LWE

**FULL PROTOCOL TITLE: The Impact of Contact Lens Coefficient of Friction (CoF) on the Development of Lid Wiper Epitheliopathy (LWE)**

		
 
• If no LWE is observed in both eyes, skip to Step 2.9: Final Evaluation and discontinue the subject from the trial
 
• If LWE is observed in either eye, continue to Step 1.1.13: Digital Photography
 

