## FULL PROTOCOL TITLE: The Impact of Contact Lens Coefficient of Friction (CoF) on the Development of Lid Wiper Epitheliopathy (LWE)

Korb LWE Grading				
Grading	Description	Height (%)	Width (mm)	Final score (grade)
0	no LWE	<25	<2	<0.25
1	mild LWE	25-50	2-4	0.25-1.00
2	moderate LWE	50-75	5-9	1.25-2.00
3	severe LWE	>75	>10	2.25-3.00

\*Final LWE score is the average of the LWE Height and Width

The tears collected by capillary tubes will be stored at -80°C until luminex multibead analysis. 15 µg of total protein will be analyzed for matrix metalloproteinases (MMP)-1, -2, -7, -9, -10. Pre- and post-contact lens wear concentrations of MMP will be compared for each subject. MMPs are a family of zinc proteases and an increase in MMP expression occurs in response to a wide range of stimuli, including adhesion molecules, growth factors, cytokines and hormones and is associated with ocular surface damage. The correlation coefficient, r, will be determined between LWE and the tear film levels of MMPs.

A  $p \leq 0.05$  will be considered statistically significant.

Layman's Description of Procedures	
Patient demographics	The subjects will be asked questions about their age, sex, race and ethnicity.
History	The subjects will be asked questions about their systemic health, ocular disease and surgical history.
Concomitant Medications	The subjects will be asked questions about their current ocular and systemic medications.
Habitual Contact Lens Information	The subjects will be asked questions about how they use their current contact lenses, such as their current contact lens brand and wear time, as performed during a normal eye exam.
Auto-refraction	A machine will shine light into a subject's eye and will estimate their prescription using different powered lenses without making contact with the eye.
Oculus Keratograph	A machine uses a video camera to determine how long it takes for a subject's tear film to

**FULL PROTOCOL TITLE: The Impact of Contact Lens Coefficient of Friction (CoF) on the Development of Lid Wiper Epitheliopathy (LWE)**

	evaporate and the height of the pooled tears between the lower lid and the ocular surface without making contact with the eye.

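### Exclusion criterion 2 gives its 0.5 cut no unit and, read in Korb component grades, lets in eyes that the protocol's own table grades as mild LWE, so eligible subjects need not be LWE-free at baseline

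*Combined protocol and SAP*

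**What the plan says.** Four places in the protocol bear on whether a subject is free of LWE at entry.

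- **Section 1.0, Objectives.** The quantity of interest is LWE "induced in subjects after contact lens fitting that do not have LWE at study enrollment".
- **Section 3.0, exclusion criterion 2.** The exclusion is for "Presence of current LWE on the upper eyelid (>0.5 in height or width"). A value of exactly 0.5 is therefore eligible. No unit or scale is given.
- **Section 3.0, screening narrative.** "If the subject does not have LWE, the subjects will be refracted to determine eligibility based on their refractive error". No cut-off is given here.
- **Section 8.0, Step 1.1.12.** The direction is reversed. Where no "LWE is observed in both eyes, skip to" the final evaluation, the subject is discontinued; a subject with LWE in either eye continues.

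The Korb table in Section 8.0 supplies the only graded definition. No LWE is a final score below 0.25, and mild LWE is 0.25 to 1.00. A footnote adds: "Final LWE score is the average of the LWE Height and Width".

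The statistical addendum names Friedman and Mann-Whitney tests for LWE staining. It mentions neither a change from baseline nor a baseline adjustment for LWE.

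**The concern.** The primary endpoint in Section 7.0 is the development of LWE after fitting. That needs a starting state, and the objective says the starting state is no LWE. If the eligibility rule lets in eyes that the grading table already labels mild, the protocol has two definitions of LWE-free.

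The practical result is easy to see. An eye with height 0.5 and width 0.5 has a final score of 0.50 at screening and passes criterion 2. If it still scores 0.50 at Day 7, the table calls it mild LWE. Nothing has changed, yet the eye entered as LWE-free and finishes with LWE.

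This is a pilot with a goal of 20 completers, intended to inform the size of a larger trial. At that size, a few such eyes could matter to a descriptive rate of LWE development.

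**Working it through.** **Inputs**

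- Eligibility (Section 3.0, criterion 2): an eye passes if height ≤ 0.5 and width ≤ 0.5.
- Final score (Section 8.0, Korb table footnote): final = (height + width) / 2.
- Bands (Korb table): none < 0.25; mild 0.25–1.00; moderate 1.25–2.00; severe 2.25–3.00.

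**Step 1. Which component step do the bands imply?** Take every height–width pair from 0 to 3 and average it.

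- Whole grades: final scores are 0, 0.5, 1.0, ..., 3.0. The band limits 0.25, 1.25 and 2.25 can never occur.
- Half grades: final scores are 0, 0.25, 0.50, ..., 3.00. These fill the bands exactly, with no gaps.
- Quarter grades: scores such as 1.125 and 2.125 arise and fall between bands.

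Half-grade components are the step that reproduces the table.

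**Step 2. Apply criterion 2 with half grades.**

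| Height | Width | Final | Korb label |
|---|---|---|---|
| 0 | 0 | (0 + 0)/2 = 0 | none |
| 0 | 0.5 | (0 + 0.5)/2 = 0.25 | mild |
| 0.5 | 0 | (0.5 + 0)/2 = 0.25 | mild |
| 0.5 | 0.5 | (0.5 + 0.5)/2 = 0.50 | mild |

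Three of the four eligible pairs are mild, and the highest eligible final score is 0.50. The table's own cut (final < 0.25) would leave only (0, 0). Two eyes of one subject could differ by up to 0.50 − 0 = 0.50 at entry.

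**Step 3. Vary the reading of 0.5, since the unit is not stated.**

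| Reading | Result |
|---|---|
| Quarter-grade components | 6 of 9 eligible pairs are mild; maximum 0.50 |
| Continuous components | mild when height + width ≥ 0.5; share of the eligible square = 1 − (0.5 × 0.5 × 0.5)/(0.5 × 0.5) = 0.5; maximum 0.50 |
| Height as a proportion (50%), width in mm | height 25–50% is grade 1, width ≤ 0.5 mm is grade 0; final (1 + 0)/2 = 0.50, mild |
| Whole-grade components | only (0, 0) is eligible; no overlap |
| 0.5% height and 0.5 mm width | both components grade 0; no overlap, but a 1 mm width, which the table grades 0 (< 2 mm), would be excluded |

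Four of the readings (half grade, quarter grade, continuous, height proportion) give the overlap and two do not. Of those two, whole grades cannot produce the table's bands, and the raw-unit reading conflicts with the table in the opposite direction.

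**The case against.** The strongest reply is that criterion 2 may itself be the working definition of LWE for screening, with the statements in Sections 1.0 and 3.0 simply referring to it. Section 8.0 ties the Korb scale to the grading of de-identified photographs; Step 1.1.12 mentions the CCLRU scale and an LWE evaluation, and nowhere is the 0.25 cut said to govern eligibility. A screening threshold above the zero of the photographic scale would then be a design preference. This is a fair reading, but it leaves two definitions in one protocol, and the unchanged 0.50 eye still crosses from one to the other.

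It is also true that the overlap depends on an unstated unit. The component-grade reading is an inference from the bands, although the best-supported one. The missing unit stands as a defect on any reading.

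Three stronger conclusions are tempting and should be resisted.

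- A reader might infer that the enrolled population was not LWE-free. The documents give no baseline LWE distribution; they show only what the rule permits.
- A reader might infer that the lens comparison is biased. The lens is assigned to the eye at random, so baseline LWE does not by itself favour either lens.
- A reader might infer that any count of eyes developing LWE is invalid. The plan specifies no such count, and baseline LWE is evaluated at Step 1.1.12 and photographed at Step 1.1.13, so prevalent and new LWE can be separated. A Friedman test across visits might bring baseline in, but the addendum does not say to which factor it is applied for LWE.

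**Conclusion.** The point holds in this form: criterion 2 has no unit and, read in Korb component grades, permits eyes with final scores of 0.25 to 0.50 that the protocol's table calls mild LWE, although the objective and the screening narrative describe subjects without it. The size is at most 0.50 of a grade per eye. How often it occurs is unknown.

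The conclusion assumes that 0.5 is a component grade (or a height proportion) and that components are scored more finely than whole grades. The harm is to any statement that LWE was induced or developed, because the addendum states no LWE change score or baseline adjustment.

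The reversed gate at Step 1.1.12 is a larger contradiction about the same eligibility condition. Correcting its direction would not settle the threshold, so both need to be resolved together. This should be fixed, and it is cheap to fix.

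**What to change.** **Definition.** Reconcile Section 1.0, criterion 2, the Section 3.0 narrative, Step 1.1.12 and the Korb table to a single definition of no LWE, per eye, with units stated. The table's own cut (final score below 0.25) would match the objective as worded. If low-grade baseline LWE is meant to be allowed, reword the objective to say so.

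**Analysis, in either case.** Use the LWE evaluation already made at Step 1.1.12:

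- report baseline scores per eye;
- count development only as an increase from that eye's baseline;
- compare lenses on paired within-subject change from baseline, or with adjustment for baseline.

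Grade baseline and follow-up by the same method. The visit tables list lid photographs at Steps 1.1.13 and 2.8 but not at Visit 1.2, so the 2-hour change may have to rest on slit-lamp grades at both times.

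**Cost.** A wording amendment and slightly more analysis work. The stricter cut could add screen failures within the allowance of 60 screened; the documents give no basis for a number. The addendum is written in the past tense, so if enrolment is complete, only the analysis and reporting part still applies.

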## **FULL PROTOCOL TITLE: The Impact of Contact Lens Coefficient of Friction (CoF) on the Development of Lid Wiper Epitheliopathy (LWE)**

7. Has significant ocular surface disease (e.g. Sjögren's Disease, Stevens-Johnson Syndrome, etc.) or significant Dry Eye Syndrome
8. Has clinically significant corneal vascularization or central corneal scaring
9. Has active ocular surface infection (e.g. conjunctivitis)
10. Has a positive history of eyelid surgery or trauma
11. Has a positive history of refractive surgery
12. Takes medications that significantly impact contact lens comfort and/or ocular surface health
13. Has taken part in another contact lens or contact lens solution clinical trial within the last 7 days
14. Is unwilling to have eyes photographed or video recorded

Potential subjects will be initially screened for study eligibility through collection of demographic data and medical history. An upper age limit for study inclusion is set at 46 years of age to 1) prevent the inclusion of presbyopic patients (i.e. those that need bifocal glasses), given that the contact lenses used in the study are single vision contact lenses and 2) reduce the number of individuals who would screen fail due to significant dry eye disease. Subjects will complete a questionnaire, the Ocular Surface Disease Index (OSDI), and subjects with a score  $\geq 23$  will be excluded from the study. A slit lamp evaluation will be performed to screen for the presence of LWE of the upper lid and for significant corneal/conjunctival staining that would prevent contact lens fitting. If the subject does not have LWE, the subjects will be refracted to determine eligibility based on their refractive error. If the refractive error is within the study specified inclusion criteria, the subject will be fit into contact lenses.

### **4.0 Vulnerable Populations**

The following vulnerable populations will be excluded from the study:

1. Adults unable to consent
2. Individuals who are not yet adults (infants, children, teenagers under the age of 18)
3. Pregnant/lactating women
4. Prisoners

The following vulnerable population may be included in the study:

1. Students for whom the principal investigators have direct access to/influence on grades.

Study subjects may be students for whom the principal investigators have access to or influence over their grades. For this reason, the principal investigators will not be responsible for recruiting or obtaining consent from students in their own

## **FULL PROTOCOL TITLE: The Impact of Contact Lens Coefficient of Friction (CoF) on the Development of Lid Wiper Epitheliopathy (LWE)**

courses in order to prevent undue influence or coercion. A study team member (e.g. study coordinator) without access to or influence on grades will be responsible for these tasks.

### **5.0 Number of Subjects**

The proposed single-site study will be conducted at The Ocular Surface Institute at the University of Houston College of Optometry. Up to 60 subjects will be screened for study inclusion, with the goal of completing 20 subjects. Subjects that screen fail may be rescreened for study inclusion up to 3 additional times at the discretion of the study investigator.

Currently, there is no information on the time from contact lens fitting to the development of LWE. This pilot study is designed to collect data which can be used to determine the sample size required to conduct a larger-scale clinical trial. It is anticipated that enrolling 20 subjects will approach the requirements of the central limit theorem for statistical analysis. Since the subjects in the study will be wearing FDA-approved contact lenses on a daily wear modality (i.e. not sleeping in contact lenses), the study does not present more than minimal risk to the subject and a power analysis is not required.

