1.1.13	Digital Photography	Perform Digital Photography of the Lid Wiper region OD/OS
1.1.14	Subjective Refraction	
Perform Manifest Refraction using maximum plus to best visual acuity.
 
 
• If the subject has <math>> 1.00\text{D}</math> refractive cylinder or greater than 1D of anisometropia, skip to Step 2.9: Final Evaluation and discontinue the subject from the trial
 

1.1.15	Subjective Spherical Equivalent Refraction	Perform Subjective Spherical Equivalent using maximum plus to best visual acuity.
1.1.16	Contact Lens Fitting	
Fit subject in contact lenses based upon the randomization schedule. Initial base curve should be selected as indicated in the fitting guide for each lens.
 
 
• If an acceptable contact lens fit cannot be obtained in either eye, skip to Step 2.9: Final Evaluation and discontinue the subject from the trial
 

1.1.17	Contact Lens Over-Refraction	Perform spherical over-refraction using maximum plus to best visual acuity
1.1.18	Contact Lens Power Adjustment (if necessary)	Modify contact lens power, based upon the Contact Lens Over-Refraction, if the subject gains 3 or more letters acuity
1.1.19	2 hour Waiting Period	Subjects released to waiting area for 2 hours

**FULL PROTOCOL TITLE: The Impact of Contact Lens Coefficient of Friction (CoF) on the Development of Lid Wiper Epitheliopathy (LWE)**

Visit 1.2 Note: Visit should be performed approximately 2 hours after lens insertion		
1.2.1	Visual Performance	Perform logMAR visual acuity
1.2.2	Oculus Keratograph	Perform the following procedures using Oculus Keratograph with the contact lens on eye, OD/OS 
 
• Non-invasive Tear Break Up Time (NITBUT)
 
• Tear Meniscus Height
 
• Video Contact Lens Fit
 

1.2.3	Ocular Surface Tear Collection	Collect 10µL surface tears using a microcapillary tube.
1.2.4	Contact Lens Removal	Remove the contact lenses and store in solution
1.2.5	Slit Lamp Exam with vital dye staining/LWE evaluation	Instill 1 drop of NaFL + Lissamine Green Combination Drop, wait 5 minutes, instill an additional drop, wait 1 minute, then evaluate slit lamp findings using the CCLRU grading scale and evaluate LWE

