## FULL PROTOCOL TITLE: The Impact of Contact Lens Coefficient of Friction (CoF) on the Development of Lid Wiper Epitheliopathy (LWE)

Visit 2: 1-Week Follow Up ( $\pm 2$ days) Note: Subjects should report to Visit 2 wearing their study assigned soft contact lenses.		
2.1	History	Collect subject history, compliance and reported wearing time
2.2	Visual Performance	Perform logMAR Visual Acuity
2.3	Questionnaires	Administer the OSDI to the subject
2.4	Oculus Keratograph	
Perform the following procedures using Oculus Keratograph (lens on eye for CL patients, bare eye for non-CL patients, OD/OS)
 
 
• Non-invasive Tear Break Up Time (NITBUT)
 
• Tear Meniscus Height
 
• Video Contact Lens Fit
 

2.5	Ocular Surface Tear Collection	Collect 10 $\mu$ L surface tears using a microcapillary tube.
2.6	Contact Lens Removal	Remove the contact lenses and store in solution
2.7	Slit Lamp Exam with vital dye staining/LWE evaluation	Instill 1 drop of NaFL + Lissamine Green Combination Drop, wait 5 minutes, instill an additional drop, wait 1 minute, then evaluate slit lamp findings using the CCLRU grading scale and evaluate LWE
2.8	Digital Photography	Perform Digital Photography of the Lid Wiper region OD/OS
Final Evaluation		
2.9	Exit Visual Acuity	Perform Distance, High Contrast Visual Acuity using Snellen optotype with the patient's habitual correction.
2.10	Final Evaluation Form	Complete the final evaluation form and indicate if the subject successfully completed the study
2.11	Protocol Deviations	Ensure any protocol deviations have been recorded

The procedures involved in the study are common clinical procedures found in Optometry/Ophthalmology. LWE assessment will occur following installation of sodium fluorescein and lissamine green ophthalmic drops. The upper and lower lids will be photographed using a slit-lamp biomicroscopy and a camera.

Photographs will be de-identified and graded subjectively for LWE using the Korb scale (see below). Photos may also be analyzed for objective LWE grading using custom coding in MATLAB.

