### **14.0 Costs/Payments to Subjects**

## **FULL PROTOCOL TITLE: The Impact of Contact Lens Coefficient of Friction (CoF) on the Development of Lid Wiper Epitheliopathy (LWE)**

There are no expected additional costs to subjects that participate in the study. There is no cost to subjects for contact lens fitting in this study. Subjects will be provided contact lenses and care solution at no cost for the duration of the study. Subjects will be provided with a token for parking at each study visit (if necessary). Subjects that complete contact lens fitting (i.e. that is completes both study Visit 1.1 and 1.2) will be compensated \$30. Subjects who complete the 1-week follow up will be compensated \$10. If subjects are determined ineligible at screening (screen fail), the subject will be compensated \$5, with the opportunity for a total of 3 re-screenings at the investigators discretion. Total subject reimbursement (without rescreening visits) will be \$40. Subjects will be compensated using Amazon electronic gift cards in the amounts indicated above, delivered to the subject via an e-mail address provided by the subject, after completion of their last study visit. Subjects who fail to complete a visit will not be compensated for that visit. Subjects will be instructed to contact the study PI in the event that they do not receive the electronic gift card.

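### Unrestricted rescreening for LWE adds a modest upward bias to the absolute amount of LWE reported as induced; the randomised lens comparison is not affected

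*Combined protocol and SAP*

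**What the plan says.** Section 5.0 of the protocol allows rescreening after any failure: "Subjects that screen fail may be rescreened for study inclusion up to 3 additional times at the discretion of the study investigator". Section 14.0 repeats the allowance in the payment terms, "with the opportunity for a total of 3 re-screenings at the investigators discretion". Neither passage sets a minimum interval, asks for a reason to expect a different result, or treats LWE failures separately.

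LWE is itself an entry criterion. Exclusion 2 in section 3.0 reads "Presence of current LWE on the upper eyelid (>0.5 in height or width". The same section says how it is judged: "A slit lamp evaluation will be performed to screen for the presence of LWE of the upper lid".

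Section 1.0 sets the objective, to "determine the amount of Lid Wiper Epitheliopathy (LWE) induced in subjects after contact lens fitting that do not have LWE at study enrollment", and section 7.0 makes the development of LWE at 2 hours and 1 week the primary endpoint. The formal hypotheses H01 and H02 in section 1.0 are narrower: they compare the two lenses at each time, with the eye for each lens assigned at random. Both eyes wear a study lens.

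The statistical addendum names Friedman and Mann-Whitney tests for LWE. It does not say which factor the Friedman test uses, and it describes no baseline adjustment and no analysis of rescreened subjects.

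**The concern.** A subjective grade varies between visits through grading error and true day-to-day change. If a subject whose usual grade is above the cut-off may try four times, a chance low reading is more likely to admit that subject, and the passing reading becomes the baseline. The next grade tends to return to the usual level with no lens effect at all.

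In a design with an untreated eye, that return could be measured and subtracted. Here it cannot. At stake are the absolute amount of LWE described as induced in subjects "induced in subjects after contact lens fitting that do not have LWE at study enrollment", and any over-time test of LWE, which the Friedman test may be.

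**Working it through.** **What the documents supply.** Up to 4 screens in all (1 + 3), a cut-off of 0.5 (read here as a grade), up to 60 screened and 20 completed. They give no repeatability of the LWE grade, no LWE distribution in the recruited population and no expected number of rescreens. There is thus no plan figure to reproduce, and all inputs below other than the cut-off and the number of screens are assumptions.

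**Step 1: chance of passing at least once.** With per-screen pass probability p, the chance over four screens is 1 − (1 − p)^4.
- p = 0.2: 1 − 0.8^4 = 1 − 0.4096 = 0.59
- p = 0.3: 1 − 0.7^4 = 1 − 0.2401 = 0.76

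**Step 2: apparent rise with no lens effect.** Simulation of 400,000 subjects. True score is normal with SD 0.6, clipped to 0–3. Each grade is the true score plus normal error, rounded to 0.5 and kept within 0–3. A subject enters at the first grade of 0.5 or less, every failure is rescreened, and the follow-up grade is drawn independently. The entries are mean follow-up minus baseline.

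| True mean | Error SD | One screen | Up to four | Added | One screen as share of total |
|---|---|---|---|---|---|
| 0.4 | 0.3 | 0.084 | 0.127 | 0.043 | 66% |
| 0.4 | 0.5 | 0.190 | 0.248 | 0.058 | 77% |
| 0.8 | 0.3 | 0.140 | 0.209 | 0.069 | 67% |
| 0.8 | 0.5 | 0.287 | 0.373 | 0.086 | 77% |

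If only one third of failures are rescreened, the totals at mean 0.8 fall to 0.168 and 0.325, so the additions are 0.168 − 0.140 = 0.028 and 0.325 − 0.287 = 0.038.

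**Step 3: a second model, and the lens comparison.** This one grades height and width in both eyes and fails the subject if any grade exceeds 0.5. It assumes total SD 0.8, population mean 0.5 or 1.0, and a stable share of variance of 0.9, 0.7 or 0.5, again with every failure rescreened and no lens effect. Trials of 20 were tested with a paired t-test in place of the rank tests.
- Apparent rise: 0.05 to 0.37 with one screen, 0.08 to 0.44 with up to four. The addition is 0.03 to 0.08 in each scenario.
- Within-eye test of change: rejects in 12–93% of trials with one screen, 25–98% with up to four.
- Between-lens difference: within 0.005 of zero. Rejection is 4.0–6.2% with one screen and 4.6–5.5% with up to four, against a nominal 5%.

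The last line is what the design implies: the subject is selected first and the eyes are assigned at random afterwards, so both lenses carry the same artefact in expectation.

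**The case against.** **The tested hypotheses are unaffected.** A reader might infer that rescreening biases the primary lens comparison. The documents do not support that, for the reason in step 3. This part of the objection stands in full. Nor is it shown that the pilot is spoiled for sizing a larger between-lens trial. That depends on the paired lens difference and its SD, and the effect of rescreening on that SD was not calculated.

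**Rescreening is not the main source.** A single low entry grade already gives 66–77% of the artefact in step 2. This stands: rescreening enlarges the problem and does not create it, and barring it leaves the larger part in place.

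**The sample is not filled with misclassified subjects.** Rescreening is discretionary and also serves failures such as an OSDI score of 23 or more, active infection or recent lens wear. In step 2 at mean 0.8, with every failure rescreened, entrants with a true score above 0.75 rise from 16% to about 29% (error SD 0.3) or from 24% to 38% (error SD 0.5). That is a shift in mix.

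**Entry grade and endpoint grade may differ.** Screening is a live evaluation, whereas section 8.0 says that de-identified photographs receive a Korb grade. That the two are the same grade is an inference. In its favour, each visit repeats the live step ("then evaluate slit lamp findings using the CCLRU grading scale and evaluate LWE"), and Visit 1.2 lists no photography, so at 2 hours the live evaluation is the only LWE assessment listed. If photographs supply both baseline and follow-up, live-grading error drops out of the artefact but true day-to-day variation remains.

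**Conclusion.** The concern holds for the absolute amount of LWE induced or developed and for any over-time test of LWE. It does not hold for H01 and H02. Under the step 2 assumptions, rescreening adds about 0.04 to 0.09 grade to an artefact of 0.08 to 0.29 grade present with one screen. The direction was upward in every scenario run. The size rests on assumed repeatability and on every failure being rescreened, and it is smaller if few LWE failures are.

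One qualification: step 1.1.12 in section 8.0 discontinues subjects with no LWE and sends those with LWE forward, opposite to sections 1.0 and 3.0. This point follows the objective and the eligibility criteria; under a literal reading of the step, selection would run the other way. Those passages must be reconciled.

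**What to change.** In section 5.0, with matching wording in 14.0, limit rescreening to failures for reasons other than exclusion 2. This brings the artefact back to the one-screen level.

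If LWE rescreening is kept, average the LWE grades from all screening attempts, apply exclusion 2 to that average and use it as the baseline. At true mean 0.8 this gives about 0.26 instead of 0.37 grade (error SD 0.5) and about 0.13 to 0.14 instead of 0.21 (error SD 0.3). The remainder persists because first-attempt passers still have a single low baseline.

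In either case, report the number rescreened for LWE, give the change-from-baseline result without them, and state that the remaining rise from a single low entry grade cannot be separated from lens-induced LWE. The addendum is written in the past tense; if enrolment is complete, these reporting steps are what can still be done.

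Cost: one sentence in 5.0, a conforming edit in 14.0 and a short addition to the analysis text. Some subjects are lost, including any whose LWE has truly cleared, and more of the 60 screening slots may be needed to complete 20.
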